addressing the transfer of acquired skills (e.g. UE motor capacity) to the performance of UE tasks during activities of daily living (ADL). The ALPS protocol will be relevant to clinical practice because it will provide clinicians with a structured, patient-centered motor learning approach to facilitate use of the paretic arm and hand. In addition, comparisons between our two intervention groups (robot-assisted therapy vs. robot-assisted therapy [RT] and task-oriented training [RT-TOT]) will add to our scientific knowledge of whether the combination of robot therapy and therapist-directed task-oriented training provides added benefit to RT alone. We will examine participant outcome measures across domains of the International Classification of Functioning (ICF)¹¹ to provide insights regarding mechanisms that underlie the recovery of motor function after stroke.

II. Specific Aims

The specific aims of this pilot study are:

Aim 1: To develop and refine a structured Active Learning Program for Stroke (ALPS) that integrates motor learning strategies with a patient-targeted home action plan to be used with either 1) robot-assisted therapy (RT) or 2) combined robot-assisted therapy and task-oriented training (RT-TOT) for the paretic arm and hand after stroke, in preparation for a larger clinical trial.

Hypothesis 1.1: RT and combined RT-TOT protocols that incorporate ALPS training will be feasible and well-tolerated by participants.

Hypothesis 1.2: After intervention, participants in both treatment groups will identify and implement a greater number of motor learning strategies during UE tasks in clinic and home settings and will report increased self-efficacy as measured by the Confidence in Arm and Hand Movement (CAHM) scale.

Aim 2: To examine effects of ALPS training and a patient-targeted home action plan combined with either 1) RT or 2) RT-TOT on paretic UE motor capacity and performance during daily activities, using *outcome measures across ICF domains*.

Hypothesis 2.1: Compared to RT alone, RT-TOT will yield similar outcomes on clinical measures of UE motor capacity (e.g. Fugl-Meyer Assessment, Wolf Motor Function Test), but greater gains on measures of UE function in the home and community (e.g. Motor Activity Log, UE accelerometry data via wearable sensors).

III. Subject Selection

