We will recruit up to 20 adults between the ages of 18 and 82 years and diagnosed with unilateral stroke more than 6 months prior to study enrollment. Stroke type will include both ischemic and hemorrhagic stroke. Eligible participants will be screened and enrolled in the study if they meet all inclusion and exclusion criteria. Protocol approval will be obtained from the SRH Institutional Review Board (IRB) and all participants will provide their informed consent prior to study participation.

Inclusion criteria:

- Moderate UE hemiparesis (i.e. some ability to move shoulder, elbow & hand and initial score on the Fugl-Meyer Assessment (FMA) between 21-50/66)

- Intact cognitive function to understand and actively engage in the ALPS robotic therapy procedures (Montreal Cognitive Assessment Score $\geq 26/30$)¹² during initial evaluation visit

Exclusion criteria:

- No more than moderate impairments in paretic UE sensation, passive range of motion, and pain that would limit ability to engage in therapy
- Increased muscle tone as indicated by score of ≥ 3 on the Modified Ashworth Scale;
- Hemispatial neglect or visual field loss measured by the symbol cancellation subtest on the Cognitive Linguistic Quick Test ¹³
- Aphasia sufficient to limit comprehension and completion of the treatment protocol
- Currently enrolled or has plans to enroll in other upper limb therapy/research during the study period
- Contraindications for robot-assisted therapy including recent fracture or skin lesion of paretic UE

IV. Subject enrollment

Recruitment Methods:

Potential subjects may be identified by the following sources:

- Printed flyers given to rehabilitation departments of local hospitals.
- Flyers posted in the outpatient clinics, therapy gyms and in public spaces inside and outside of the hospital.
- The Partners RSVP for health website.
- Contact with support groups and conferences.
- Research recruitment emails, for example Spaulding Rehabilitation Network Research Recruitment emails, and Social Medias.
- Contact to patients listed in the Partners Research Patient Data Registry (RPDR).
- Stroke Survivors who previously volunteered to be contacted about opportunities to participate in research studies at SRH may be contacted by phone by a study staff.
- Attending physicians and therapists may refer their stroke inpatients/outpatients to the study. We will provide the physicians with study flyers.

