Specifically, the informed consent will be obtained by the principal investigator ([name]) or [name], Research Coordinator/Manager in the Motion Analysis Lab at SRH. The testing and intervention protocol will be described and the research space and equipment will be shown to the subject. Study staff will clearly explain all procedures and risks of the protocol outlined in the informed consent form (ICF). The subject will be given adequate time to consider his/her decision and encouraged to ask questions, both during the initial interview and throughout the study. A member of the study staff will answer any questions regarding the study at the time consent is given. Enrollment will begin when the subject thoroughly understands and signs the informed consent form. Participants will be provided with a signed copy of the completed consent form. Once enrolled, the subject may pause or terminate his/her participation at any time during the study. Participants will be randomized to one of two treatment groups (robot-assisted therapy [RT] or robot-assisted therapy plus task-oriented training [RT-TOT]) according to a randomization sequence prepared by [name].

V. Study Procedures

Study procedures will occur in the Motion Analysis Lab (MAL). The study involves up to 24 visits in total to be completed within a 16 week period. The total duration may vary within this 16 week period to accommodate missed study visits.

1. MAL Visit Day 1: Screening and enrollment
2. MAL Visit Days 2-3: Baseline outcomes assessment battery. We will equip participants with Actical wearable sensors for home-based accelerometry data collection.
3. MAL Visit Days 4-21: Intervention. We will retrieve Actical wearable sensors at after baseline data collection at the onset of intervention visits.
4. MAL Visit Days 22-23: End-of-intervention outcomes assessment battery. We will equip participants with Actical wearable sensors for home-based accelerometry data collection.
5. MAL Visit Day 24: Follow-up outcomes assessment battery. We will equip participants with Actical wearable sensors for home-based accelerometry data collection.

Schema 1: study procedures flow

- 1) MAL Visit Day 1: Screening and enrollment** (procedures described in section IV)
- 2) MAL Visit Days 2-3: Baseline outcomes assessment battery** (administered within a 2-3 week period before intervention). **Equip with Actical wearable sensors.**

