The clinical assessment session will last approximately 1 ½ to 2 hours, and the standardized measures listed in Table 1 will be administered. All are reliable and valid measures of UE motor capacity and function. Minimal detectable change scores have been reported for the FMA,¹⁴ Motor Activity Log,¹⁵ and Stroke Impact Scale.¹⁶ The clinical evaluator will be blinded to the participants' group assignment and study hypotheses.

Kinematic data indicative of movement quality will be collected via 3-D motion capture (Vicon Motion Systems Ltd. UK) in the Motion Analysis Laboratory (MAL) during reach/grasp tasks with the paretic arm. Variables of interest may include index of curvature (IOC) (ratio of actual distance the hand travels to the most direct distance), movement smoothness (number of times hand trajectory = 0 during reach), trunk displacement (degrees of movement in sagittal, planar, and transverse planes), and interjoint coordination (range of angular motion at the shoulder, elbow and wrist).^{17,18} The kinematic testing protocol will be collaboratively developed by [name] and [name] and his MAL staff. This may include reach and grasp movements directed toward targets positioned in front of the subject to elicit functional movements, including upward reach, forward reach, shoulder abduction, shoulder rotation, pronation of the forearm, wrist extension, and finger flexion/extension. We anticipate that this quantitative assessment will require an additional 1-1/2 hour/session at baseline and discharge.

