Surface electromyographic (SEMG) data may be gathered during the kinematic testing protocol above to study the characteristics of muscle activation patterns in stroke survivors during the performance of arm reaching movements. Data will be collected using Cometa WavePlus wireless surface electrodes with 16 channels (www.cometasystems.com) for the detection of EMG activity from muscles that are involved in the performance of upper extremity movements. We will follow the SENIAM (Surface Electromyography for the Non-Invasive Assessment of Muscles) guidelines to place electrodes on several muscles involved in the performance of the arm reaching movements. Muscles may include the following: rhomboid major, latissimus dorsi, infraspinatus, superior trapezius, deltoid - anterior part, deltoid - medial part, deltoid - posterior part, pectoralis major, clavicular head, triceps brachii, lateral/medial heads, biceps brachii (short heads), biceps brachii (long heads), brachialis, brachioradialis, pronator teres, extensor carpi radialis and extensor carpi ulnaris. The EMG on the back, shoulder, upper arm and forearm will be attached using bio-adhesive double sided tape and secured with Coban.

We may ask permission from study participants to video record them during the performance of the above-described clinical tests and the lab-based assessments.

Home Based Accelerometry – Wearable Sensors: The Actical physical activity monitoring system (<http://www.philips.com>) is a multi-directional, waterproof sensor used to quantitatively measure UE activity during everyday living situations. Sensors will be worn on both wrists during 72-hour periods at each assessment point to allow comparisons between paretic and intact UE activity in the home/community.¹⁹ A single page user guide for the wrist sensors will be provided to participants, and sensors may be removed at any time due to discomfort. There will be no penalty for loss or damage to a wrist sensor, subjects will be given a pre-stamped envelope to return the Actical at the end of the 72-hour period. Staff in [name] Analysis Laboratory (MAL) at SRH have used this device and will analyze de-identified raw data in order to examine changes in arm movement pre- to post-intervention (e.g. the amount and laterality of use).

The proposed assessment timeline is below (Table 1).

ICF Domain/Assessments	Baseline	Discharge	1-month Follow-up
UE Function:			

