The tasks selected for the home action plan (HAP) will be based on the participant's identified upper extremity (UE) goals and/or therapist input based on a) the current focus of robot therapy (i.e. shoulder/elbow, hand) and b) scores on the FMA key form. Because of this participant-centered approach there will be no core tasks included in every HAP, however, similarities may be observed across individuals. Participants will identify an UE task to be completed at home and the ALPS strategy or strategies they will use to facilitate performance weekly. A brief self-report questionnaire to collect ordinal data on ALPS strategy use, HAP performance, frequency, & perceived difficulty will be administered by research staff after every 3rd therapy session. Participant's engagement in the home action plan will be rated using a 3 point Likert type scale²⁹ and patient-targeted UE tasks will be updated as needed. A similar questionnaire will be administered during the follow-up assessment to gain information regarding the participant's engagement in home practice after formal therapy has ended. Participants will be instructed that completion of the HAP is voluntary and will not affect their therapy in any way. The intent of the HAP is to provide documentation of home carry-over. It is not designed to be a comprehensive home exercise program.

4) MAL Visit Days 22-23: End-of intervention outcomes assessment battery
(administered at discharge assessment after 18 treatment sessions) **Equip with Actical wearable sensors.**

The same assessment battery as the one performed at baseline will be re-administered.

5) MAL Visit Day 24 (Final Visit): Follow-up outcomes assessment battery
(administered at 1 month post-therapy) **Equip with Actical wearable sensors.**

The same assessment battery as the one performed at baseline will be re-administered, **except for** the Motion Capture and EMG analysis.

VI. Biostatistical Analysis

Separate repeated measures analyses of variance (2 group x 3 time points) will examine changes in scores for each outcome measure across a) baseline, b) discharge and c) follow-up assessments. Descriptive statistics will be used to compare key group characteristics, including age, hand dominance, side of lesion, and years of education. Group comparisons will be assessed by chi-square analyses for categorical data and t-tests for continuous data. The data collected from this pilot study may be used for a power analysis of a larger clinical trial.

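### Section VI's 2 x 3 repeated-measures ANOVA yields no single arm difference with a CI for Hypothesis 2.1 and cannot be fitted to motion capture/SEMG; a baseline-adjusted model on scores already scheduled is a cheap, modest improvement

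*Combined protocol and SAP*

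**What the plan says.** Section VI is one short paragraph. Its outcome analysis reads: "Separate repeated measures analyses of variance (2 group x 3 time points) will examine changes in scores for each outcome measure". The three time points are baseline, discharge and follow-up. The section names no arm contrast, visit of interest, CI, baseline covariate, sphericity correction or rule for missing outcomes. The chi-square and t-tests follow the sentence on group characteristics and name no treatment contrast. The section adds that the data may feed the power analysis of a larger trial.

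The hypotheses to be served are in Section II:

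- Hypothesis 2.1 compares the arms: "Compared to RT alone, RT-TOT will yield similar outcomes on clinical measures of UE motor capacity", but "greater gains on measures of UE function in the home and community". The Fugl-Meyer and Wolf tests are examples of the first kind of measure, and the Motor Activity Log and wrist accelerometry of the second. No visit or margin is given.
- Hypothesis 1.2 concerns change within each arm: participants "will report increased self-efficacy as measured by the Confidence in Arm and Hand Movement (CAHM) scale".

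The remaining facts:

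- Section III: "We will recruit up to 20 adults between the ages of 18 and 82 years". This is a ceiling, and no allocation ratio is stated.
- Section V, on motion capture: "We anticipate that this quantitative assessment will require an additional 1-1/2 hour/session at baseline and discharge". Table 1 agrees, and the text for visit Day 24 leaves motion capture and EMG out.
- Section IV: "the subject may pause or terminate his/her participation at any time during the study".
- Section V, on accelerometry: "sensors may be removed at any time due to discomfort". The same paragraph allows for a lost or damaged sensor.

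**The concern.** Four features of the plan cause difficulty.

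1. Baseline is a response level, although randomisation makes it a natural covariate. The group main effect then averages in a visit at which no treatment effect can exist.
2. The group-by-time interaction is the relevant test. It has 2 df and returns an F and a p-value, not one arm difference with its uncertainty.
3. Classical repeated-measures ANOVA usually keeps only participants with every visit, and no other rule is given. One lost sensor record would remove that person's remaining accelerometry scores, on one of the two measures named for the expected advantage of RT-TOT.
4. Section VI applies a three-visit model to every outcome, but motion capture/SEMG has two visits.

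With at most 20 participants, the useful between-arm result is an estimate with its CI, which is also what a later power analysis needs. A non-significant F on the motor-capacity measures would not show that the arms are similar.

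**Working it through.** The documents give no alpha, SD, correlation, effect size or missing rate, so there is no planned figure to reproduce. What follows is illustration. **Assumed:** 10 per arm (the ceiling of 20, split equally), unit SD, two-sided 5% level, and equal correlation rho between visits unless stated otherwise.

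**Step 1, schedule.** Section VI needs three time points for each outcome. Motion capture/SEMG has two by the text and Table 1 of Section V. The stated model cannot be fitted there, and this needs no assumption.

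**Step 2, group main effect.** With a true arm difference d at both post-treatment visits and none at baseline, the main effect estimates (0 + d + d)/3 = 2d/3. For d = 0.8 that is 0.53.

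**Step 3, precision of the discharge arm difference (n = 10 per arm, N = 20).**

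- Change score: variance = 2(1 - rho) x 2/n, on 18 df.
- Baseline-adjusted: variance = (1 - rho²) x (2/n) x (1 + 1/(N - 4)), on 17 df.
- Ratio, adjusted to change score = (1 + rho)/2 x 17/16.

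| rho | Ratio | Mean simulated 95% half-width, adjusted | Same, change score |
|---|---|---|---|
| 0.5 | 0.75 x 1.0625 = 0.797 | 0.83 SD | 0.93 SD |
| 0.7 | 0.85 x 1.0625 = 0.903 | 0.68 SD | 0.72 SD |
| 0.85 | 0.925 x 1.0625 = 0.983 | 0.50 SD | 0.51 SD |

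The ratio is 1 when 1 + rho = 2 x 16/17 = 1.882, that is, rho = 0.88.

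**Step 4, power (complete data, 0.8 SD at both post-treatment visits, 40,000 replicates).** For rho 0.5/0.7/0.85 the planned F(2,36) has 41/62/91% and the discharge ANCOVA 47/63/87%. The difference is about +6/+1/-4 points, so there is no general gain.

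**Step 5, type I error.** Under equal correlations the planned F holds 4.9-5.1%. Now let discharge and 1-month scores correlate 0.9 with each other and 0.7 with baseline:

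- uncorrected F: 6.3% (4.9% with Greenhouse-Geisser);
- discharge-minus-baseline contrast with the ANOVA's pooled error: 8.5%;
- the same contrast with its own error term, which is the change-score t-test on 18 df: about 5%;
- discharge ANCOVA: 5.0%;
- mixed model: 5.4%.

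Across all its settings the mixed model's type I error was 4.8-5.8%. With 4,000 replicates each, the simulation standard error is sqrt(0.05 x 0.95/4000) = 0.34 points.

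**Step 6, retention.** Suppose each post-baseline visit is missed independently with an assumed probability m. Expected complete cases are 20(1 - m)², and participants with at least one post-baseline score are 20(1 - m²). For m = 5/10/15/20% these are 18.1/16.2/14.4/12.8 against 20.0/19.8/19.6/19.2.

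The cost of discarding people from the adjusted discharge comparison follows from (4/N)(1 + 1/(N - 4)):

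- N = 20: 0.2125
- N = 19: 0.2246, ratio 1.06
- N = 18: 0.2381, ratio 1.12
- N = 17: 0.2534, ratio 1.19

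The simulated ratio of complete-case to mixed-model variance, with 3 of 20 missing only the 1-month visit at random, was 1.19-1.25.

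**The case against.** The strongest objection is that one added sentence would do most of the work: name the discharge-minus-baseline contrast, give it its own error term, and use everyone with those two scores. That is a valid single arm difference with a CI, and it keeps a participant who misses only the 1-month visit. This stands, and it limits the point in two ways. The 8.5% type I error belongs only to a pooled-error contrast, which Section VI does not specify. The 19-25% variance loss belongs only to listwise deletion with an assumed 3 of 20 missing. Neither figure counts against this alternative.

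The plan also limits missing data. Missed therapy appointments are rescheduled, and the 16-week window has slack. Sensors come with a guide and a prepaid return envelope, and straps can be adapted for comfort. Early removal of a sensor may shorten a record without losing it. This stands too, so the missing rate could be low. It does not supply a rule for the scores that are missing.

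The motion capture/SEMG mismatch can be read as a slip for a 2 x 2 analysis, and SEMG is optional. That is a reasonable guess at the intent, but the plan should say it.

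Finally, this is a pilot whose first aim is development and feasibility. A new model does not choose a primary outcome or visit, set a margin for similarity, or deal with the ordinal Modified Ashworth score. All of that is true.

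**Conclusion.** The point holds as a modest, inexpensive improvement. From the text alone: baseline is a response level, no arm difference with a CI is specified for Hypothesis 2.1, no missing-outcome rule is given, and the stated model does not fit motion capture/SEMG. Listwise deletion is the method's usual behaviour, not something the plan states.

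Over a named contrast with its own error term on available data, the gain is precision only: about 20%, 10% and 2% less variance at assumed correlations of 0.5, 0.7 and 0.85, and none near 0.88 and above. The documents do not give the correlation.

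A reader might infer three stronger conclusions that the documents do not support:

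- That the planned test is invalid. It is valid under sphericity, and a Greenhouse-Geisser correction restores its level otherwise.
- That the change buys power. Against ANCOVA on the mean of both post-treatment visits, the F compares as 41% v 64% at rho 0.5 and 0.8 SD. That assumes an equal effect at both visits and a visit choice the plan has not made. At discharge alone the difference runs from +6 to -4 points.
- That the mixed model cures the loss of sensor data. A lost baseline record still removes that person from the adjusted accelerometry analysis, as does having no score after baseline.

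**What to change.** Reword Section VI as follows.

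- Analyse discharge and 1-month scores in a mixed model with arm, visit, arm-by-visit and the participant's own baseline score as covariate, unstructured covariance and small-sample degrees of freedom.
- Include every randomised participant with a baseline and any post-baseline score, in the assigned arm, and state that this is valid under missing at random.
- Report the adjusted arm difference with 95% CI at discharge and at 1 month. Name in advance which outcome and visit test the expected advantage on home and community measures. The choice is the sponsor's: discharge alone misses an effect that appears only at 1 month, and an average of both visits loses power if the effect fades.
- For motion capture/SEMG, use ANCOVA of the discharge score on baseline.
- For the motor-capacity measures, report the estimate and CI, and do not read non-significance as similarity.
- Keep each arm's mean change from baseline, with CI, for the CAHM part of Hypothesis 1.2.

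The cost is a rewritten paragraph, with no new measures or visits. The covariate takes one df, and the analysis rests on missing at random. Precision can fall slightly: if the post-treatment SD is 1.3 times baseline at rho 0.7, the adjusted variance is 1.69 x 0.51 x 1.0625 = 0.916 against 1.69 + 1 - 2 x 0.7 x 1.3 = 0.87 for the change score, about 5% larger. If the sponsor prefers to keep the ANOVA, the minimum is the named contrast with its own error term and CI, an available-data rule, and a two-visit analysis for motion capture/SEMG.
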